- 5. Proportion of patients actively on OAC at 12 months of follow-up
- 6. Incident rate of hospitalization for any bleeding
- 7. All-cause in-hospital mortality rates
- 8. All-cause mortality rates among patients with accurate out-of-hospital mortality data (such as Medicare Advantage patients)
- 9. Health care utilization for AF patients, which would be reported as counts of number of health care utilization events (outpatient visits, days hospitalized, number of emergency department visits, etc.)

C. EXPLORATORY OBJECTIVES

The exploratory objectives are to:

- 1. Evaluate the effect of the early and delayed education interventions on primary and secondary endpoints over the course of the follow-up through the date on which at least 80% of eligible study participants have at least 24 months of follow-up time.
- 2. Explore the CTTI and the FDA supported Sentinel Data Partnership's ability to successfully conduct a pragmatic trial to answer important questions to improve public health.

VI. STUDY DESIGN AND DURATION

The study is a prospective, randomized, and open-label education intervention trial. Patients with AF and a CHA₂DS₂-VASc score of 2 or greater will be randomized in a 1:1 ratio to an early intervention cohort and a delayed intervention cohort within each participating health plan. The definition for OAC medication fill will be an OAC medication dispensing or at least 4 INR tests in the claims data.¹ The claims records of the patients randomized to the early intervention cohort will then be linked to "fresh" (i.e. about 1-4 months old) pharmacy claims data at the time of randomization. Patients without evidence of an OAC medication fill during the 12 months prior to randomization will be included in the patient-level and provider-level early educational intervention (patients randomized to this early intervention with evidence of an OAC medication fill during the 12 months prior to randomization will be excluded from the trial.). In addition to usual care, these patients and their providers² will receive a

¹Not all OAC dispensings are well captured in pharmacy claims, particularly, for warfarin. INR tests are assumed indicative of OAC fills that were not billed through the claims. 4 INR tests or values within a 12-month period will be used as a proxy since that is roughly the number of tests administered in the process of stabilizing dose.

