The providers of patients in the delayed cohort who did not receive OAC medication during the course of the 12-month study period and meet our inclusion criteria will receive the delayed intervention: the provider-only education intervention, a one-time mailing administered 12 months after at least 80% of early intervention mailing have occurred (patients will not receive any educational materials unless no provider can be identified for a mailing). We intend to assess the primary and secondary endpoints again once at least 80% of patients have at least 24 months of follow-up time to assess the durability and longer-term outcomes of the effect of the patient- and provider-level education intervention, as well as the use of OAC following the delayed provider-level education intervention. However, as this second assessment is exploratory, we may not conduct these analyses if the results of the primary outcome are null.

Because the Sentinel Distributed Database will be used for follow-up information, and this information is refreshed approximately quarterly and this is done on separate timetables for the different health plans, it is likely that when at least the required follow-up time is available for at least 80% of people, there will be more than 12 or 24 months of follow-up for over 80% of people. All participants' outcomes will be assessed using all possible person-time; patients will have different duration of follow-up and that will be accounted for in the analyses.

A schematic diagram below shows the design of the early intervention period of the study over the course of the follow-up through the date on which at least 80% of eligible study participants have at least 12 months of follow-up time:

^{*}Baseline characteristics of delayed and early intervention cohorts will be taken from the same time point at randomization from a dataset that is archived at randomization, while exclusion criteria for evidence of OAC medication fill or P2Y12 antagonist use was determined at randomization for the early intervention cohort and approximately 12 months post-randomization for the delayed intervention cohort.

[figure not shown]
For analysis, treatment status is at time of randomization or corresponding early intervention mailing; for the delayed intervention mailing it is prior to mailing.

^{**}All possible person-time will be used to assess participants' outcomes (patients will have different duration of follow-up).

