The waiver of informed consent is consistent with the approach that has been taken in several similar clinical trials, the first using individual patient randomization, the others cluster randomized:

- 1. UH3 Pragmatic Trial of Population-based Programs to Prevent Suicide Attempt (NCT02326883)
- 2. The HMO Research Network CERT: A randomized trial of direct-to-patient communication to enhance adherence to beta-blocker therapy following myocardial infarction (NCT00211172)
- 3. MI FREE: A Randomized Evaluation of First-dollar Coverage for Post-MI Secondary Prevention Therapies (NCT00566774)
- 4. STOPCRC: Strategies and Opportunities to Stop Colon Cancer in Priority Populations (NCT01742065)

XIII. INDEPENDENT ADVISORY COMMITTEE

An independent advisory committee (IAC), consisting of members independent from the study team and with expertise in statistics, anticoagulation for atrial fibrillation, engagement, health plan management, and/or in practical clinical trials, will serve to enhance patient safety and trial integrity. The IAC will meet with study leadership at least twice. The first meeting will occur before intervention materials are mailed, and the second will take place two months after all mailings are sent. In addition, other meetings will occur if deemed necessary by the IAC chair, study leads and/or the FDA. The study team will provide the IAC with the study protocol before any intervention materials are mailed and will brief the IAC on any issues (or lack thereof) that have been raised 2 months after the last mailing has occurred. The IAC will advise on concerns that arise. An IAC charter describes the roles, responsibilities, and operations of the IAC.

XIV. STATISTICAL CONSIDERATIONS

A. SAMPLE SIZE AND POWER CALCULATIONS

Our target sample size is 80,000 patients. All enrolled patients and/or their providers will be targeted by mailing (early or delayed) provided they are eligible at time of mailing and able to be contacted.

1. Primary Endpoint

The following assumptions were used to determine the sample size and power for the primary endpoint assessing the proportion of AF patients with evidence of at least one OAC prescription fill through the date on which at least 80% of eligible study participants have at least 12 months of follow-up time:

- 33% OAC initiation rate in the delayed intervention arm over the first year of the study

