 - In a Sentinel feasibility assessment of identified health plan members meeting similar inclusion and exclusion criteria as this trial, 33% had evidence of OAC initiation in a 1 year period of follow-up.
- 38% OAC initiation rate in the early intervention arm (a 5% absolute improvement in OAC initiation over the 33% OA initiation expected in the delayed intervention arm over 1-year follow-up)
- 1-year attrition rate: 30% dropout or lost-to-follow-up
- Two-sided type I error of 0.05
- Roughly 10,000 patients (Table below) will yield more than 99% power to detect a 5% absolute difference

[figure not shown]

Power	Total sample size (2-arm)	Early Intervention	Delayed Intervention
90%	5610	2805	2805
95%	6910	3455	3455
99%	9718	4859	4859

Total Number of Patients in a 2-arm study (Unadjusted for dropouts)

OAC Initiation Endpoint (33% Control Rate), continuity corrected Chi-square

2. Important Secondary Analysis of Stroke or TIA

A study with approximately 80,000 patients is well powered for the outcome of stroke or TIA over the course of the follow-up through the date on which at least 80% of eligible study participants have at least 12 months of follow-up time, under certain assumptions listed below:

- 1-year stroke or TIA rate: 18% among patients not treated with OAC
- 1-year stroke or TIA rate: 7% among patients treated with at least 1 OAC fill
- Duration of follow-up: 1 year
- 33% of delayed intervention patients will have at least 1 fill of OAC, meaning the 1 year stroke or TIA rate in the delayed intervention group would be 14.4%
- If 38% of early intervention patients have at least 1 fill of OAC (meaning the 1 year stroke or TIA rate in the early intervention group would be 13.82%, i.e., an absolute reduction of 0.55%), the study will have 46% power to detect this 0.55% reduction. However, if 40.5% of early intervention patients have at least 1 fill of OAC (meaning the 1 year stroke or TIA rate in the early intervention group would be 13.54%, i.e., an absolute reduction of 0.83%), the study will have 80% power to detect this 0.83% reduction.

- 1-year attrition rate: 30% dropout or lost-to-follow-up
- Two-sided type I error of 0.05

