- Health care utilization, reported as counts of number of health care utilization events (outpatient visits, days hospitalized, number of emergency department visits, etc.)

Depending on the review of preliminary data, the primary endpoint and some secondary endpoints may be examined separately by warfarin and novel OAC. This will be descriptive only and will not include formal statistical testing.

C. EXPLORATORY ENDPOINTS

We will evaluate the effect of the early and delayed education interventions on the primary and secondary endpoints once at least 80% of eligible study participants have at least 24 months of follow-up time (the early intervention includes mailing to the patient and provider while the delayed intervention, at approximately 12 months follow-up, only includes a provider mailing). Note that we may

¹ Data for out of hospital mortality are not available

not conduct these analyses if the results of the primary outcome are null in the 12-month follow-up assessment. Therefore, this statistical analysis plan does not include the details of analyses for a 24-month assessment.

D. DATA SOURCE

The data used for the study are claims data from the five participating sites, transformed into the Sentinel Common Data Model. At the time of analysis, the data available in the Sentinel Distributed Database (i.e., those approved and in use for Sentinel routine surveillance activities) will be used to assess the primary and secondary endpoints.

As background, the identification and creation of the study cohort was based on the claims data in the Sentinel Distributed Database plus linked “fresh” data (i.e., about 1 month old) for pharmacy claims and enrollment information. The target population for the study was those members enrolled in the sites who did not have evidence of an OAC medication dispensing in the 12 months prior to randomization; the fresh and production data ensured we identified those eligible for the trial. The data used for routine Sentinel activities are several months old – hence the need for certain “fresh” data – and the date of the last available claims varies by site.

E. PATIENT INCLUSION CRITERIA

All inclusion and exclusion criteria were determined by claims data. For entry into the study, the following criteria **MUST** be met at the date of randomization:

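### The 24-month early-versus-delayed comparison cannot show durability, because the delayed arm's providers are mailed at about 12 months and a lasting effect could look smaller

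*Protocol*

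**What the plan says.** Protocol VI plans to assess the primary and secondary endpoints again once at least 80% of patients have 24 months of follow-up, "to assess the durability and longer-term outcomes of the effect of the patient- and provider-level education intervention". It adds a second aim, to look at anticoagulant (OAC) use after the delayed provider letter. The Study Design entry of the synopsis also gives durability as the purpose.

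The same section mails the providers of delayed-arm patients who are still untreated and still eligible, in "a one-time mailing administered 12 months after at least 80% of early intervention mailing have occurred". Patients themselves receive materials only where no provider can be identified. Protocol VI defines the primary outcome as a comparison of the early with the delayed arm. Protocol XIV.B and SAP II use all person-time and list the censoring events; the delayed mailing is not one of them.

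The exploratory objective in Protocol V.C reads "Evaluate the effect of the early and delayed education interventions on primary and secondary endpoints", and SAP I.C says "We will evaluate the effect of the early and delayed education interventions on the primary and secondary endpoints". Neither mentions durability. SAP I.C explains that the early intervention goes to patient and provider, and the delayed one, at about 12 months, to the provider only. Both documents allow the 24-month analysis to be dropped if the primary result is null, and SAP I.C gives no methods for it.

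**The concern.** A durability claim needs a comparator that stays on usual care. For roughly the second year there is none, because every eligible untreated delayed-arm patient is due for a mailing.

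The primary endpoint makes this harder to see. At least one fill is cumulative, so it cannot fade within a patient; only the gap between the arms can shrink. It shrinks a little anyway as both arms keep starting treatment, and it shrinks further with each start caused by the delayed letter. Neither is fading. The same difficulty reaches the longer-term outcomes, since those extra starts could change stroke and bleeding rates in the comparator.

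The second aim has a related limit. There is no concurrent unmailed group, so OAC use after the delayed letter is a before-after description.

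Protocol XVII plans a separate manuscript for the 24-month results, if that analysis is run, and their return to each Data Partner. A narrowed gap could therefore be published as a loss of effect when the early effect had lasted.

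**Working it through.** **Reproducing the plan's own figure.** The documents give no figure for the 24-month contrast. The 12-month rates used here are those behind the sample size table in Protocol XIV.A.1 and SAP I.G.1: "33% OAC initiation rate in the delayed intervention arm over the first year of the study", "38% OAC initiation rate in the early intervention arm", "Two-sided type I error of 0.05" and "1-year attrition rate: 30% dropout or lost-to-follow-up". For 90% power, per arm:

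- n = [1.960·√(2·0.355·0.645) + 1.282·√(0.33·0.67 + 0.38·0.62)]² / 0.05² ≈ 1,923
- with continuity correction, (n/4)·[1 + √(1 + 4/(0.05n))]² ≈ 1,963
- divided by 0.70 for attrition, 2,805, so 5,610 in total

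For 95% and 99% power, 2,418 and 3,401 per arm become 3,455 and 4,859, so 6,910 and 9,718 in total. All three totals match. (They match only after the division by 0.70, although the Protocol labels the table as unadjusted for dropout. That does not bear on this point.)

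**24-month illustration.** Two inputs are not in the documents and are assumptions:

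- h, the share of still-untreated patients who start in year 2 under usual care: 5%, 10% or 15%
- m, the extra share of untreated delayed-arm patients who start because of the letter: 0, 3 or 5 points

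The early arm's 12-month gain is kept in full:

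- early = 0.38 + 0.62h
- usual care = 0.33 + 0.67h
- delayed arm with letter = 0.33 + 0.67(h + m)

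The true gap is 0.05 − 0.05h. The planned contrast is that gap minus 0.67m, which is 2.01 points at m = 3 and 3.35 points at m = 5.

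| h | Gap to usual care (also the contrast at m = 0) | Contrast, m = 3 points | Contrast, m = 5 points |
|---|---|---|---|
| 5% | 4.75 | 2.74 | 1.40 |
| 10% | 4.50 | 2.49 | 1.15 |
| 15% | 4.25 | 2.24 | 0.90 |

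Share hidden: 0% at m = 0; 2.01/4.75 = 42% to 2.01/4.25 = 47% at m = 3; 3.35/4.75 = 71% to 3.35/4.25 = 79% at m = 5.

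**Fewer patients mailed.** The table treats the whole untreated 67% as mailed. If the planned 30% attrition is applied to all year-2 starts (assumption), the true gap is 0.05 − 0.05·0.7h, or 4.83 to 4.48 points. The letter removes 0.67·0.7·m, or 1.41 points at m = 3 and 2.35 at m = 5. The hidden share for m = 3 to 5 becomes about 29–52%.

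**Cross-check with another model.** Express the early effect as the share of otherwise untreated patients who start: 1 − 0.62/0.67 = 7.46%. Let the delayed letter have a fraction f of that strength, so that delayed = 1 − 0.67(1 − h)(1 − 0.0746f). At h = 10%:

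- f = 0: 44.2% versus 39.7%, 4.50 points
- f = 0.5: 44.2% versus 42.0%, 2.25 points
- f = 1: 44.2% in both arms, 0 points

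The gap falls in proportion to f. The last case is a limit, since it gives a provider-only letter the full strength of the patient-and-provider package. The distortion is a bias, so 80,000 patients do not cure it.

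**The case against.** The strongest reply is that neither document says in so many words that the early-versus-delayed gap at 24 months is the durability measure. The aim in Protocol V.C and SAP I.C covers both interventions, SAP I.C already describes them correctly, and the 24-month methods are unwritten. This stands in part: SAP I.C needs little or no change. But the synopsis and Protocol VI say that repeating endpoints defined as a between-arm comparison will assess durability, and no rule separates the delayed arm's response. That is more than missing detail.

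Second, the letter's effect has no source. Protocol X says there is no current evidence that insurer communications of this kind change OAC use. This stands, so zero belongs in the range. A reader might infer that a lasting effect is bound to look faded; the documents do not support that. Still, the analysis may be dropped after a null primary result, so it would mainly be run when the early mailing had worked. Some effect of the provider letter is then more plausible, although the delayed mailing normally lacks the patient component.

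Third, active OAC use at 12 months is already a secondary endpoint (Protocol V.B), so a cut at the delayed mailing adds little. The overlap is real. However, SAP II.D.3 measures active use at the end of follow-up, and SAP Table 6 restricts it to patients treated for at least one day, which selects on a post-randomization outcome.

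Fourth, mailing the delayed arm is deliberate, because every eligible untreated patient is meant to receive an intervention. That is accepted. The point concerns what the contrast is said to show, not the mailing.

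**Conclusion.** The concern holds as a matter of interpretation. After about month 12 the contrast compares an early patient-and-provider mailing with a later provider-only mailing, and it cannot separate fading from catch-up. With 38% versus 33% at 12 months, an early effect kept in full and h of 5–15%, between 0% and about 79% of a 4.25–4.75 point effect would be hidden. The upper end assumes a 5-point letter effect in all untreated patients; attrition or lost eligibility lowers it.

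Two stronger inferences should be avoided. A reader might conclude that the 24-month result would point the wrong way, but the early arm stays ahead in every row of the table. A reader might also conclude that the primary result is compromised. It is not: the delayed mailing comes at the end of the 12-month period that the primary analysis is meant to cover, and the 24-month analysis is exploratory and optional. The change is worth making because it alters what the trial can claim and costs little.

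**What to change.** 1. In the synopsis (Study Design) and Protocol VI, remove durability as what the 24-month between-arm comparison shows. There and in Protocol V.C item 1, describe the contrast as early patient-and-provider mailing versus provider-only mailing about 12 months later, in line with SAP I.C.
2. Base any randomized durability statement on active OAC use by arm in all modified intention-to-treat patients, not only those treated for at least one day. Cut both arms no later than each Data Partner's recorded delayed-mailing date, and state that this covers only about 12 months.
3. Report early-arm persistence after that date, and delayed-arm OAC use after its letter, as descriptive and without a causal claim.

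The cost is wording in the protocol, one recorded mailing date per Data Partner, and one further run of the planned active-OAC analysis with a different denominator and cut. The documents do not give the mailing dates, but each Data Partner does its own mailing and can record them. No 24-month methods exist in the SAP to be undone. The downside is that no randomized durability claim can be made beyond the delayed mailing, which the design could not support in any case.

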Atrial fibrillation (AF) is the most common arrhythmia seen in clinical practice, accounting for one-third of rhythm-related hospitalizations. The prevalence of AF in the United States is 1% overall and more than 10% in people over age 80 years, with approximately 70% of cases in patients between 65 and 85 years of age. As Americans age, the number of patients with AF is expected to increase 150% by 2050, with more than 50% of patients being octogenarians or older. The increasing burden of AF is expected to lead to a higher incidence of stroke, as patients with AF have a five to seven fold greater risk of stroke than the general population. Patients with a stroke in AF patients is 4 to 5% per year. Patients with a stroke due to AF have worse prognoses than patients with stroke without AF. All Oral anticoagulants (OACs) are an important therapy for patients with AF as they decrease the rate of stroke by more than two-thirds.

The clinical benefit of warfarin is only seen in patients who consistently maintain their international normalized ratio (INR) values within the therapeutic range (2.0-3.0). ¹⁶ The median times in the therapeutic range in the ARISTOTLE¹⁷, ROCKET AF¹⁸, RE-LY¹⁹, and ENGAGE²⁰ trials were 62%, 55%, 64%, and 68%, respectively. As part of quality improvement efforts, there is significant interest in measuring and improving performance of physicians in prescribing anticoagulation for patients with AF. The CHADS₂ and CHA₂DS₂-VASC scores have been developed to support providers in identifying patients with AF who are at an increased risk for stroke. ^{21,22} Paradoxically, anticoagulation use is no higher, or declines, as the risk of stroke, as measured by these scores, increases. ²³ This is in large part due to the fact that physicians and patients are concerned about the risk of bleeding in higher-risk populations, and they may underappreciate the net benefit from anticoagulants, including stroke prevention. In any case, approximately 40-60% of patients with AF at risk of stroke are not prescribed anticoagulation therapy. ^{15,24-30} This translates to over 50,000 preventable strokes each year in the United States with a number needed to treat of approximately 25 patients to prevent 1 stroke.

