- The sample size has 80% power to detect a 0.5% absolute reduction in stroke, assuming a cumulative 1-year incidence of stroke of 4.2% in control (delayed intervention arm) patients and 3.7% in intervention (early intervention arm) patients. The assumption is that patients not on oral anticoagulation have an annual stroke rate of 5%, and stroke will be reduced by 50% (HR=0.5) in the treated (anticoagulated) population. The 80% power requires that 52% of early intervention arm patients are treated at 1-year as compared to 33% in the control arm.

B. POPULATIONS FOR ANALYSIS

All analyses will be based on a modified intention-to-treat principle (i.e., all identified early intervention patients who meet eligibility and are mailed the intervention will be included; using "pseudo" wave assignments, all identified delayed intervention patients who meet eligibility at the time of corresponding early mailings will be included in the analysis). The primary endpoint will be calculated based on the proportion of patients with evidence of at least one OAC prescription fill over the course of the follow-up through the date on which at least 80% of eligible study participants have at least 12 months of follow-up time. An as-randomized analysis will be performed for the primary endpoint as a sensitivity analysis. All possible person-time will be used to assess participants' outcomes; patients will have different duration of follow-up and that will be accounted for in the analyses. Patients will be censored from the analysis at the time of death, disenrollment from the health plan, loss of medical or pharmacy coverage, or change in eligibility for inclusion in research based on health plan membership. The statistical analysis plan (SAP) provided more information and outlines in detail how granular aggregate data will be received from each Data Partner in lieu of patient-level data.

XV. OUTCOME DEFINITIONS

All outcome definitions will be based on available claims data.

- 1. Evidence of OAC start: the proportion of AF patients who have at least 4 INR values measured or who fill at least one OAC prescription for apixaban, dabigatran, edoxaban, rivaroxaban, or warfarin over the course of the follow-up through the date on which at least 80% of eligible study participants have at least 12 months of follow-up time

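### The stroke/TIA power rests on unsourced 18%/7% rates that the same list's stroke assumptions (5%, hazard ratio 0.5) do not support; the stated 46% and 80% hold only under the first set

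*Protocol*

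**What the plan says.** Protocol XIV.A.2 bases the stroke-or-TIA power on "1-year stroke or TIA rate: 18% among patients not treated with OAC" and "1-year stroke or TIA rate: 7% among patients treated with at least 1 OAC fill". It mixes these rates by uptake. In the control arm, "33% of delayed intervention patients will have at least 1 fill of OAC", which gives a stated 14.4%. At 38% uptake in the early arm the stated rate is 13.82% and the power 46%. The 80% figure applies only "if 40.5% of early intervention patients have at least 1 fill of OAC", with a stated rate of 13.54%. Two-sided alpha is 0.05, follow-up is one year and attrition is 30%.

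The last bullet of the same list covers stroke alone. It sets the untreated rate at 5% a year and takes it that "stroke will be reduced by 50% (HR=0.5) in the treated (anticoagulated) population". It gives 80% power for 52% against 33% uptake.

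The protocol synopsis and SAP I.G.2 repeat both sets. The secondary objectives (Protocol V.B) make both outcomes hospitalizations. The wording on adequacy varies: XIV.A.2 calls the trial well powered subject to its assumptions, the synopsis says reasonably powered, and the SAP says only that reasonable power is possible.

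**The concern.** The two sets of inputs sit in one list, apply to the same patients over the same year, and concern nested outcomes. If they share a definition, the gap between them must be patients with a TIA hospitalization and no stroke. That gap is 13% a year in untreated patients against 5% for stroke itself. The implied treatment effect also differs, at about 65% on TIA-only events and 50% on stroke. Neither figure is stated or sourced, whereas the 33% initiation rate is attributed to a Sentinel feasibility assessment.

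Power is at stake for the first-listed secondary objective, which the plan itself labels important. The 0.55 and 0.83 percentage-point reductions, and hence the 46% and 80%, scale with the 18% and depend on the 7/18 ratio. If the composite rate lies closer to the stroke rate, a null stroke-or-TIA result would be read against a power the trial did not have.

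**Working it through.** **Inputs (Protocol XIV.A.2; same in SAP I.G.2).** Untreated and treated stroke-or-TIA rates 18% and 7%; untreated stroke rate 5% with hazard ratio 0.5; uptake 33% (control) against 38% or 40.5% (early); 80,000 patients randomized 1:1 with 30% attrition, so 40,000 × 0.70 = 28,000 per arm; two-sided alpha 0.05.

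**Step 1: reproduce the plan.** Arm rate = u × (1 − f) + t × f, where u and t are the untreated and treated rates and f is uptake.
- Control: 0.18 × 0.67 + 0.07 × 0.33 = 14.37%
- Early, 38%: 0.18 × 0.62 + 0.07 × 0.38 = 13.82%
- Early, 40.5%: 0.18 × 0.595 + 0.07 × 0.405 = 13.545%

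Power = Φ(d/SE − 1.96), where d is the difference between arms and SE its standard error (two-proportion test).
- 38%: d = 0.0055, SE = 0.002941, so Φ(1.870 − 1.960) = 46.4% (stated 46%)
- 40.5%: d = 0.00825, SE = 0.002929, so Φ(2.817 − 1.960) = 80.4% (stated 80%)

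Both stated powers are reproduced. The stroke-alone figure is also consistent: 4.175% against 3.70% gives about 82% (stated 80%).

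**Step 2: set the inputs side by side, assuming one shared definition.**
- Untreated TIA without stroke: 18% − 5% = 13%; 13/5 = 2.6 times the stroke rate
- Treated: 7% − 2.5% = 4.5%
- Implied treatment effect on TIA-only events: 1 − 4.5/13 = 65%
- Treatment effect on stroke: 50%
- Treatment effect on the composite: 1 − 7/18 = 61%

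A patient with both events counts once, so the 13% means TIA and no stroke.

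**Step 3: vary the untreated composite rate.** The documents give no TIA rate, so the rates below 18% are assumptions; 5% is the floor (no TIA-only events). There are 28,000 patients per arm throughout. The treated rate is u × 7/18 (the plan's composite ratio) or u × 0.5 (the plan's stroke effect).

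| Untreated composite | 38% uptake, ratio 7/18 | 38% uptake, HR 0.5 | 40.5% uptake, ratio 7/18 | 40.5% uptake, HR 0.5 |
|---|---|---|---|---|
| 18% (plan) | 46% (stated 46%) | 32% | 80% (stated 80%) | 62% |
| 12% | 32% | 22% | 61% | 43% |
| 10% | 27% | 19% | 53% | 37% |
| 8% | 22% | 16% | 44% | 30% |
| 6% | 17% | 13% | 34% | 23% |
| 5% | 15% | 11% | 29% | 20% |

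Example (8%, HR 0.5, 40.5%): arm rates 6.68% and 6.38%, d = 0.0030, SE = 0.002088, so Φ(1.437 − 1.960) = 30%.

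The 18% row with HR 0.5 uses only figures in the plan, and power still falls from 80% to 62%.

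**Step 4: uptake needed for 80% power.** The plan needs 40.5%. For an untreated composite of 10% down to 5%, the need is about 43-48% with the 7/18 ratio and 46-51% with HR 0.5.

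**The case against.** A composite may exceed its component, so 18% and 5% do not contradict each other in logic. The 13% follows only if both rates share one definition. The XIV.A.2 bullets for stroke or TIA do not say hospitalization, and SAP Appendix C, whose list is marked as not final, includes broad cerebrovascular codes. A wide claims definition for one rate and a narrower one for the other could explain part of the gap. That stands, and it is why the 13% is conditional. It does not remove the problem: the objectives define both outcomes as hospitalizations, and the same appendix places the TIA codes inside ischemic or unknown stroke, which would bring the two outcomes closer together.

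The 5% and the hazard ratio of 0.5 carry no source in XIV.A.2 either. The Introduction puts the effect of anticoagulation on stroke at more than two-thirds, which is nearer to 61% than to 50%. Its "stroke in AF patients is 4 to 5% per year" describes AF patients in general, not untreated patients with a score of 2 or more, so it gives the 5% only weak support. A reader might infer that the 18% is the wrong figure, or that the trial's true power is some single lower value. The documents support neither: they show a conflict and do not say which side is right. Nor is there an arithmetic error.

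The plan also discloses much of the weakness. It states only 46% power at the design uptake of 38%, and its wording is conditional. That is fair, but both stated powers rest on the same 18% and 7%, so the disclosure is itself conditional on them.

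**Conclusion.** The point holds as one of inconsistent assumptions. The stated 46% and 80% are correct for 18%/7% and 28,000 per arm, but the plan does not reconcile those inputs with the 5% and hazard ratio of 0.5 in the same list. At every assumed composite rate from 5% to 12%, under either of the list's two treatment effects, power at 40.5% uptake is between 20% and 61%, not 80%. At 38% uptake it is between 11% and 32%, not 46%. These ranges depend on the assumed composite rate, which the documents do not fix. The unconditional part is that the 13% gap, if the definitions match, is unexplained, and that using the plan's own stroke effect with its own 18% already lowers the two powers to 62% and 32%. The primary endpoint is not affected.

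**What to change.** Derive the stroke rate, the stroke-or-TIA rate and the effect of anticoagulation on each from one source and one outcome definition. There are two candidates:
- The Sentinel feasibility cohort already cited for the 33%, followed forward.
- The pooled, both-arm claims rate in the year before randomization. This needs a caveat: eligibility removes patients who died, had an intracranial hemorrhage or started an anticoagulant, so the baseline-year rate may misstate follow-up risk.

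Then restate the arm rates (14.4%, 13.82%, 13.54%) and the conditional powers in the protocol synopsis, XIV.A.2 and SAP I.G.2, and align the wording on adequacy across the three. Until that is done, replace the well-powered statement in XIV.A.2 with the range of power over plausible composite rates, showing the assumed treatment effect and uptake for each. Adding a citation for the 18% alone would not be enough unless it also explains the gap to the 5%.

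The cost is one descriptive query that does not compare arms, plus rewording in three places. The downside is a less favourable stated power for this secondary outcome. Sample size, primary endpoint, analyses and conduct stay as they are.
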